9.2 Randomization

A randomization schedule will	be computer-generated before the start of the study.

MM-II

Safety Analysis Set

The Safety Analysis Set will include all randomized subjects who received the single dose of IP. Analyses will be based on the actual treatment received.

9.5.4 Pharmacokinetic Analysis Set

The PK Analysis Set will include all subjects in the

9.6 Endpoints

9.6.2 Primary Efficacy Endpoint

[figure not shown]
The primary efficacy endpoint is:

• The change from Baseline in the WOMAC A pain score at Week 12.

9.6.3 Secondary Efficacy Endpoints (up to Week 26)

The secondary efficacy endpoints are as follows:

• To assess the effect of a single IA joint injection of MM-II in subjects with symptomatic OA as measured by the change from Baseline for:

These parameters will be assessed using the PK Analysis Set.

9.7 Description of Statistical Analyses

[figure not shown]
9.7.1 General Statistical Methods

Summary statistics will be presented by treatment group. For continuous variables, unless otherwise stated, the number of available observations (n), mean, SD, median, and range will be provided. For categorical variables, the number and percentage in each category will be displayed.

Assessments of change from Baseline to post-Baseline will include only those subjects with both Baseline and post-Baseline measurements. The last value of a variable taken before the single dose of IP will be used as the Baseline value. Unless otherwise specified, missing or dropout data will not be imputed for the purpose of data analysis.

A more detailed description of study analyses will be presented in the SAP that will be finalized before the sample size reassessment.

9.7.2 Analysis of Primary Endpoint

Protocol	CLR	17	17
			_

 $Amendment\ 2-18\ Jun\ 2021$

MM-II

Physical Examination

10 DIRECT ACCESS TO SOURCE DATA/NOTES

The Investigator/institution shall provide direct access to source data/documents for study-related monitoring, audits, IEC/IRB review and regulatory inspection.

11 QUALITY CONTROL AND QUALITY ASSURANCE

11.1 Conduct of the Study

Sponsor and CRO shall implement and maintain quality control and quality assurance procedures with written Standard Operating Procedures and study manuals to ensure that the study is conducted and data are generated, documented and reported in compliance with the protocol, ICH GCP R2 and applicable regulatory requirements.

This study shall be conducted in accordance with the provisions of the Declaration of Helsinki (October 2013)¹⁰, Food and Drug Administration (FDA) (CFR, Sections 312.50 and 312.56), EU (Annex 1, Directive 2001/83/EC) and UK regulations (The Medicines for Human Use [Clinical Trials] Regulations 2004 [no.1031]), and with ICH GCP R2 (CPMP 135/95).

The Investigator may not deviate from the protocol without a formal protocol amendment having been established and approved by an appropriate IEC/IRB, except when necessary to eliminate immediate hazards to the subject or when the change(s) involve(s) only logistical or administrative aspects of the study. Any deviations may result in the subject having to be withdrawn from the study and render that subject non-evaluable.

11.2 Study Monitoring

The Investigator shall permit the Sponsor/designated CRO Site Monitor to review study data as frequently as deemed necessary to ensure that data are being recorded in an adequate manner and that protocol adherence is satisfactory.

The Investigator will provide access medical records for the monitor in order that entries in the eCRF may be verified. The Investigator, as part of his/her responsibilities, is expected to co-operate with Sponsor/designated CRO in ensuring that the study adheres to GCP requirements.

12 ETHICS

12.1 Independent Ethics Committee/Institutional Review Board

Prior to the start of the study, the Investigator is responsible for ensuring that the protocol and consent form have been reviewed and approved by a relevant IEC/IRB. The IEC/IRB shall be appropriately constituted and perform its functions in accordance with FDA, ICH GCP and local requirements as applicable.

The IEC/IRB shall approve all protocol amendments, written informed consent forms and document updates, subject recruitment procedures (e.g., advertisements), written information to be provided to the subjects, Investigator's Brochure, available safety information, the Investigator's curriculum vitae and/or other evidence of qualifications and any other documents requested by the IEC/IRB and Regulatory Authority (Competent Authority) as applicable.

12.2 Written Informed Consent

The nature and purpose of the study shall be fully explained to each subject (or their legally responsible guardian).

Written informed consent must be obtained from each subject (or guardian) prior to any study procedures being performed. The process of obtaining informed consent must be documented in the subject source documents.

The consent documents to be used for the study shall include all the elements of informed consent as outlined in accordance with FDA, ICH GCP and local requirements as applicable and be reviewed and approved by the appropriate IEC/IRB prior to use.

Protocol CLR	17	17
--------------	----	----

 $Amendment\ 2-18\ Jun\ 2021$

MM-II

13 DATA HANDLING AND RECORD KEEPING

13.1 Case Report Forms/Source Data Handling

All required study data must be entered in the eCRF created for the study. This data collection tool is a validated electronic data capture (EDC) system that contains a system generated audit trail. Data required according to this protocol are recorded by investigational site personnel via data entry into the internet based EDC software system. The Investigator shall ensure that all data from subject visits are promptly entered into the eCRFs in accordance with the specific instructions given. The Investigator must sign each eCRF to verify the integrity of the data recorded. All internal Sponsor/designated CRO and external investigational site personnel seeking access to the eCRF are supported by the CRO data manager. At the end of the study all data captured electronically will be provided to the Investigator for archiving at the investigational site.

A list of the normal ranges for all laboratory tests to be undertaken forms part of the documentation to be collated prior to study start. If a central laboratory has been selected to conduct any or all tests, it is essential that all samples be analyzed at that laboratory, unless otherwise specified (e.g., ESR).

The Investigator must maintain source documents, such as laboratory reports, X-rays, ECGs, consultation reports, and complete medical history and physical examination reports. All information in the eCRF must be traceable to the source documents in the subject's file.

13.2 Retention of Essential Documents

The Investigator/institution should maintain the study documents as specified in the ICH guidelines on GCP and as required by the applicable regulatory requirements. The Investigator/institution should take measures to prevent accidental or premature destruction of these documents.

Essential documents should be retained until at least 2 years after the last approval of a marketing application in an ICH region and until there are no pending or contemplated marketing applications in an ICH region or until at least 2 years have elapsed since the formal discontinuation of clinical development of the IP. These documents should be retained for a longer period, however, if required by the applicable regulatory requirements or by an agreement with the Sponsor. It is the responsibility of the Sponsor to inform the Investigator/institution as to when these documents no longer need to be retained.

The Sponsor shall carry an insurance policy to cover compensation of subjects' health injuries arising from the study. If a subject incurs a study-related injury, the subject may be treated (and other necessary measures taken) at the study site and/or another medical institution. If it is necessary to compensate for the treatment, the Sponsor will cover the cost. The Sponsor shall not impose on the subject the burden of proving the causal relation between the study and the injury.

If any of the following is confirmed, the Sponsor may refuse or restrict the payment of the compensation:

- 1. A serious GCP or protocol deviation by the Investigator or Sub-Investigator (except deviation medically necessary to avoid an immediate hazard to the study subjects)
- 2. Intentional act or negligence on the part of the Investigator or Sub-Investigator or malpractice thereby
- 3. Injury caused by unlawful act or delinquency of a third party
- 4. Injury caused by intentional act or negligence of the subject

If compensation becomes necessary for a study-related injury, the site will promptly notify the Sponsor and will co-operate with the Sponsor and its insurer (or their legal representatives) in their handling thereof.

15 PUBLICATION POLICY

The Sponsor shall retain the ownership of all data. When the study is complete the Sponsor shall arrange the analysis and tabulation of data. A clinical study report shall then be prepared, which may be used for publication, presentation at scientific meetings or submission to regulatory authorities. All proposed publications based on this study must be subject to the Sponsor's approval requirements.

The Sponsor assures that the key design elements of this protocol will be posted in a publicly accessible database such as clinicaltrials.gov.

MM-II (

16 CONFLICT OF INTEREST POLICY

The independence of this study from any actual or perceived influence, such as by the pharmaceutical industry, is critical. Therefore, any actual conflict of interest of persons who have a role in the design conduct, analysis, publication, or any aspect of this study will be disclosed and managed. Furthermore, persons who have a perceived conflict of interest will be required to have such conflicts managed in a way that is appropriate to their participation in the study. The study leadership in conjunction with the Sponsor has established policies and procedures for all study group members to disclose all conflicts of interest and will establish a mechanism for the management of all reported dualities of interest.

18 APPENDIX

18.1 SYNOPSIS OF AMERICAN COLLEGE OF RHEUMATOLOGY CRITERIA FOR OSTEOARTHRITIS

(https://www.rheumatology.org/Portals/0/Files/Idiopathic%20OA%20of%20the%20Knee.pdf)

Clinical and laboratory	Clinical and radiographic	Clinical		
Knee pain	Knee pain	Knee pain		
+at least 5 of 9	+at least 1 of 3	+at least 3 of 6		
-Age >50 years	-Age >50 years	-Age >50 years		
-Stiffness <30 min	-Stiffness <30 min	-Stiffness <30 min		
-Crepitus	-Crepitus	-Crepitus		
-Bony tenderness	+Osteophytes	-Bony tenderness		
-Bony enlargement		-Bony enlargement		
-No palpable warmth		-No palpable warmth		
-ESR <40 mm/hour				

18.2 WOMAC SCALE

PATIENT NAME

WESTERN ONTARIO AND M CMASTER OSTEOARTHRITIS INDEX (WOMAC) Please circle the appropriate rating for each item.

ricase dide de appropriae radig ou cadinelli.						
RATE YOUR PAIN WHEN	NONE	g_KSHT	MODERATE	severe	EXTREME	HOSPITAL USE ONLY
Walking	0	1	2	3	4	
Climbing stairs	0	1	2	3	4	
Steeping at night	0	1	2	3	4	
Resting	0	1	2	3	4	
Standing	0	1	2	3	4	TOTAL
RATE YOUR STIFFNESS IN THE	NONE	алант	MODERATE	66YERE	ежтеме	HOSPITAL USE ONLY
Morning	0	1	2	9	4	
Evening	0	1	2	3	4	TOTAL
RATE YOUR DIFFICULTY WHEN	NONE	алант	MODERATE	GENERE	EXTREME	HOSPITAL USE ONLY
Descending stairs	0	1	2	3	4	
Ascending stairs	0	1	2	3	4	
Rising from sitting	0	1	2	3	4	
Standing	0	1	2	3	4	
Bending to floor	0	1	2	3	4	
Walking on even floor	0	1	2	3	4	
Getting involutor car	0	1	2	3	4	
Going shopping	0	1	2	3	4	
Putting on socks	0	1	2	3	4	
Rising from bed	0	1	2	3	4	
Taking off socks	0	1	2	3	4	
Lying in bed	0	1	2	3	4	
Getting involution teath	0	1	2	3	4	
Sitting	0	1	2	3	4	
Getting on/off toilet	0	1	2	3	4	
Doing light domestic duties (cooking , dusting)	0	1	2	3	4	
						I I

0

2

3

4

TOTAL

WORLD TOTAL SCORE

YAMAPAI REGIONAL MEDICAL CENTER PHYSICAL REHABLITATION SERVICES

Doing heavy domestic duties (moving furniture)

WOMAC OSTEOARTHRITIS INDEX QUESTIONNAIRE

PERMANUTATION OFFICE OF PT THATKA WORK O CASE OTTO NAME PER MRS 4000 (11475)

EWEVED BY PHYSIOAL THERASIST

NTENTO(QNUTURE

ADAMTS	A disintegrin and metalloproteinase with thrombospondin motifs
AE	Adverse event
AESI	Adverse Event of Special Interest
ANCOVA	Analysis of covariance
ATC	Anatomical Therapeutic Chemical
AUC	Area under the concentration-time curve from time zero to time of last quantifiable concentration
BMI	Body mass index
C _{max}	Maximum observed concentration
COX II	Cyclooxygenase II
CS	Clinically significant
CTCAE	Common Terminology Criteria for Adverse Events
CTX	C-terminal crosslinking telopeptide of collagen
CV	Coefficient of variation
DMPC	Dimyristoylphosphatidylcholine
DPPC	Dipalmitoylphosphatidylcholine
ECG	Electrocardiogram
eCRF	Electronic case report form
EoS	End of Study
FAS	Full Analysis Set
huARGS	Aggrecanase degraded aggrecan
IA	Intra-articular
IP	Investigational product
LLOQ	Lower limit of quantification
MedDRA	Medical Dictionary for Regulatory Activities
MACE	Major adverse cardiovascular event
MMPs	Matrix metalloproteinases
MMRM	Mixed model repeated measures
NCS	Not clinically significant

	CLR_17_17 Statistical Analysis Plan	
	Date: 30-Sep-2022	Page 7 of 28

Abbreviation	Definition
NSAIDs	Non-steroidal anti-inflammatory drugs
OA	Osteoarthritis
PC	phosphatidylcholines
PK	pharmacokinetic
PN	Preferred name
PPAS	Per Protocol Analysis Set
PT	Preferred term
PtGA	Patient Global Assessment
SOC	System organ class
SD	Standard deviation
TEAE	Treatment emergent adverse event
T _{max}	Time to maximum observed concentration
VAS	Visual Analog Scale
WHO	World Health Organization
WOMAC	Western Ontario and McMaster Universities Osteoarthritis Index

	CLR_17_17 Statistical Analysis Plan	
	Date: 30-Sep-2022	Page 8 of 28

1. INTRODUCTION

1.1 Background

Osteoarthritis (OA) is the most common form of joint diseases, and is characterized by articular cartilage degradation, osteophyte formation, bone remodeling, joint space narrowing, and joint inflammation. It is estimated that 80% of the population will have radiographic evidence of OA by the age of 65 years, although only 20% of those will be symptomatic. The etiology of OA is unknown, but is believed to be multifactorial, including hereditary, metabolic causes, mechanical damages, and inflammatory in nature. Osteoarthritis of the knees has higher prevalence than any other joints. Clinical manifestations of OA in the knees include pain in and around the joint, particularly on weight-bearing of the knee joint, stiffness of the joint after rest, and limited joint motion due to pain and/or stiffness of the joint. The end result of all forms of OA is often loss of function of the joint or limb, imposing significant economic burden on the individuals as well as the society. Diagnosis of OA is based on signs and symptoms, and is often confirmed with imaging studies or using laboratory tests to rule out concomitant inflammatory causes. Since the pathophysiology of OA is unknown, current recommendations for managing OA focus on relieving pain and stiffness, and improving physical function as important goals of therapy. Non-surgical treatment of OA focuses on reducing overloading of joints, physiotherapy, and alleviation of pain and inflammation, usually by topical, systemic, or intra-articular (IA) joint administration of drugs.

Currently available medication regimens for most OA include non-opioid analgesics such as acetaminophen/paracetamol, nonsteroidal anti-inflammatory drugs (NSAIDs), and injectable hyaluronic acid. These pharmaceutical agents can provide transient pain relief quite effectively, but long-term use of NSAIDs has been found to be associated with increased risk of gastrointestinal bleeding, hypertension, cardiovascular events, congestive heart failure, and renal insufficiency, etc. Long-term opioid use for OA is generally discouraged due to lack of information on benefits as well as risks of addiction and other side effects. The NSAIDs in the form of topical application and cyclooxygenase II (COX II) inhibitors are considered somewhat safer than other NSAIDs in terms of gastrointestinal side effects, although COX II inhibitors are contraindicated in patients with a history of coronary artery disease. Because of the high incidence of side effects associated with long-term therapy of both nonselective and COX II selective NSAIDs, effective and safer alternative treatments for OA are urgently needed.

MM-II is composed of two surface active phospholipids

1.2 Study Design

This is a randomized, double-blind, placebo-controlled, single administration, multiple-dose, Phase IIb study to evaluate the efficacy of MM-II administered by a single IA joint injection of either MM-II or placebo in subjects with symptomatic knee OA. The study has been developed based on design features used in the completed first-in-human study for the symptomatic knee OA indication. The primary efficacy endpoint is based on the change from Baseline of Western Ontario and McMaster Universities Osteoarthritis Index (WOMAC) A pain score. Secondary efficacy endpoints are based on evaluation of other measures of pain scores, disease activity scores, and weekly cumulative exposure to rescue medication, which are all accepted measures for the evaluation of clinical outcome.

1.3 Rationale

Osteoarthritis of the knees is the most common form of arthritis, both inflammatory and non-inflammatory in nature, particularly after the age of 45. The pathophysiology of OA is poorly understood. Therefore, currently available medication regimens for OA, including non-opioid analgesics such as acetaminophen/paracetamol and NSAIDs, focus on providing transient palliative anti-inflammatory and pain-relieving benefits for OA, as opposed to curative effects. However, long-term use of these agents is associated with a wide range of side effects involving multi-organ systems. Furthermore, these agents have often provided limited and temporary pain relief. Therefore, effective and safer alternative treatments for OA are urgently needed. This Phase IIb, randomized, double-blind, placebo-controlled, single-administration, multiple-dose study is designed to demonstrate the efficacy and safety of MM-II for treatment of knee pain, and to identify an optimal dose in a large population of subjects with symptomatic knee OA. The subjects in the proposed study will receive a single IA joint injection of either MM-II or placebo. Specifically, subjects will be randomized to one of the following treatment arms:

- Arm A: MM-II 1 mL IA joint injection,
- Arm B: MM-II 3 mL IA joint injection,
- Arm C: MM-II 6 mL IA joint injection,
- Arm D: Placebo 1 mL IA joint injection,
- Arm E: Placebo 3 mL IA joint injection, or
- Arm F: Placebo 6 mL IA joint injection.

2. STUDY OBJECTIVES AND ENDPOINTS

Primary Efficacy Objective	Endpoint(s)
To determine the optimal dose of an IA joint injection of MM-II in the treatment of knee pain in subjects with symptomatic knee OA	Change from Baseline of WOMAC A pain score at Week 12
Primary Safety Objective	Endpoint(s)
To assess the safety and tolerability of a single IA joint injection of MM-II in the treatment of knee pain in subjects with symptomatic knee OA at Week 12	
• AEs• Laboratory assessments• Vital signs• ECG• Physical examination

Secondary Objectives	Endpoint(s)
To assess the effect of a single IA joint injection of MM-II in subjects with symptomatic OA	
• [REDACTED]• [REDACTED]• Change from Baseline in the weekly average of daily knee pain scores by Visual Analog Scale (VAS) at Weeks [REDACTED] 26, [REDACTED]• Change from Baseline in the weekly average of daily global pain scores by VAS at Weeks [REDACTED] 26, [REDACTED]
[REDACTED]	[REDACTED]

3. PRIMARY ESTIMAND

Primary Estimand	
Primary scientific question of interest	What is the optimal dose of a single IA joint injection of MM-II as compared to placebo in the treatment of knee pain in subjects with symptomatic knee OA?
Target Population	Defined through appropriate inclusion/exclusion criteria as listed in the study protocol.
Treatments of Interest	
• Single IA joint injection of 1 mL MM-II• Single IA joint injection of 3 mL MM-II• Single IA joint injection of 6 mL MM-II
Outcome Variable	Change from Baseline in WOMAC A pain score at Week 12
Summary Measure	Least square mean difference between active doses and 3 mL placebo and associated p-values from a mixed model repeated measures (MMRM) with fixed effects for treatment, visit, and treatment-by-visit interaction and covariates site, Baseline WOMAC A pain score, and randomization stratification factors adjusting for multiplicity using Dunnett's step-down procedure
Intercurrent Events	No adjustments to the primary estimand will be made based on intercurrent events

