- 25. Female subjects of childbearing potential who do not agree to practice established effective methods of contraception, for example, a combination of the following: (1) oral contraceptive, depo progesterone, or intrauterine device; and (2) a barrier method (condom or diaphragm). Male subjects with female partners of childbearing potential must ensure that their female partners use highly effective birth control as described above and a barrier method of contraception (e.g., condom) if not surgically sterile (i.e., vasectomy). Contraceptive methods must be practiced for the entire study duration. If a subject discontinues prematurely, the contraceptive method must be practiced for 12 weeks following final administration of IP. A follicle stimulating hormone (FSH) test should be performed to confirm menopause for those women with no menses for less than 1 year.
- 26. Female is pregnant or breast feeding, or planning to become pregnant or initiate breastfeeding while enrolled in the study.
- 27. Subject will not be available for protocol-required study visits, to the best of the subject's and Investigator's knowledge.
- 28. Subject previously has been randomized in this study or has previous received treatment with MM-II.
- 29. Donation or loss of 400 mL or more of blood within 12 weeks before dosing.
- 30. Subjects who have been placed in an institution on official or judicial orders.
- 31. Subjects who are related to or dependent on the Investigator, Sponsor, or study site such that a conflict of interest may arise.
- 32. Have a condition or be in a situation which, in the investigator's opinion, may put the subject at a significant risk, may confound study results, or may interfere significantly with the subject's participation in the study. This criterion provides an opportunity for the investigator to exclude subject based on clinical judgment, even if other eligibility criteria are satisfied.

Reference Therapy, Dose and Duration of Administration:

injection with a sampling window of +/- 60 minutes from the time of IP-injection.

Pharmacodynamics:

Safety: The following information will be collected for assessment of safety:

- Laboratory assessments
- Vital signs
- Electrocardiogram
- Physical examination
- The weekly cumulative amount of rescue medication

Statistical Methods:

Sample Size: ~ 348

Approximately 348 subjects will be randomized following screening in this study. The randomization allocation ratio would be initially.

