he randomization will be centralized over all sites.

Approximately 348 subjects are expected to result in the approximate following subjects' allocations:

[Arm A] MM-II, 1 mL IA joint injection

[Arm B] MM-II, 3 mL IA joint injection

[Arm C] MM-II, 6 mL IA joint injection

[Arm D] Placebo, 1 mL IA joint injection

[Arm E] Placebo, 3 mL IA joint injection

[Arm F] Placebo, 6 mL IA joint injection

With approximately 72 evaluable subjects per arm for the primary endpoint (Arms A, B, C, and E), the study is powered at 80% with an alpha level of 0.05 assuming a baseline WOMAC A (0-4; mean of 5 questions) pain score of 2.0 with standard deviation of 0.59 and a change from Baseline in the WOMAC A pain score of 0.52 (26%) and 0.8 (40%) for placebo and MM-II, respectively, yielding a difference of 0.28 between the groups.

For primary efficacy endpoint will be analysed with Mixed Effect Model (MMRM) with fixed effects for treatment group, study visit, treatment-by-visit interaction, site and baseline covariates. Subject will be included as random effect. Treatment differences will be estimated for all Active Arms (A, B, C) vs Placebo 3 mL arm (E) will be estimated via least square means from the analysis model along with 95% confidence intervals, and associated 2-sided p-values

The study will begin with the sample size yielding at least 80% power under an optimistic scenario assuming SD = 0.59. After 80% of the study subjects are enrolled, the assumptions for SD will be re-

MM-II

checked in blinded fashion, and the sample size could be increased. The sample will not be increased more than a maximal total of N=609. If increase in the sample size is required post blinded sample size re-estimation, enrolment of the additional patients after accrual of 348 patients would be done using an allocation ratio of 3:3:3:1:3:1. Enrolment for the study will then continue until the new target sample size is reached. The enrolment size at each site will be capped at no more than 20% of the overall sample size.

MM-II

TABLE OF CONTENTS

1	SIGNA	ATURE I	PAGES	2
	1.1	SPONS	SOR SIGNATURE PAGE	2
	1.2	Genera	l Information	3
	1.3	Signatu	re of Investigator	4
2	STUD	Y SYNO	PSIS	5
TABL	E OF CO	ONTENT	TS	14
LIST (OF TAB	LES		18
LIST (OF ABB	REVIAT	TIONS AND DEFINITION OF TERMS	19
3	INTRO	DDUCTI	ON	22
	3.1	Backgr	ound	22
	3.2	Discuss	sion of Study Design	23
	3.3	Rationa	ale	23
		3.3.1	Rationale for Dose	24
		3.3.2	Rationale for Study	25

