3.3.4 Statistical Justification

Statistical analysis for the primary endpoint will be based on comparison of the change from baseline between the treatment groups. The comparison will be done by longitudinal mixed effect model (MMRM) with fixed effects for treatment group, study visit, treatment-by-visit interaction, site and baseline covariates.

Approximately 348 subjects are expected to result in the approximate following subjects' allocations:

[Arm A] MM-II 1 mL IA joint injection

[Arm B] MM-II 3 mL IA joint injection

[Arm C] MM-II 6 mL IA joint injection

[Arm D] placebo 1 mL IA joint injection

[Arm E] placebo 3 mL IA joint injection

[Arm F] placebo 6 mL IA joint injection

approximately evaluable subjects per arm for the primary endpoint the study provides 80% power with an alpha of 0.05.

STUDY OBJECTIVES

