4. STATISTICAL METHODOLOGY

4.1 General Principles

All collected study data will be presented in listings. All derivations and statistical analyses will be performed using SAS® software Version 9.4. Prior and concomitant medications will be coded using World Health Organization (WHO) Drug Dictionary Enhanced September 1, 2020. Adverse events (AEs) and medical history will be coded using Medical Dictionary for Regulatory Activities (MedDRA) Version 23.1.

Unless stated otherwise, descriptive summaries for continuous variables will include n (number of subjects with non-missing results), mean, standard deviation (SD), median, minimum, and

maximum. For categorical variables, n and percent will be provided. Percentages will be calculated out of the number of subjects in the given population with a non-missing result.

Nominal outcome summaries, presented by collection day and/or by time point, will be based on scheduled assessments as planned in the protocol. Unscheduled assessments will be presented in listings and will not be included in the analyses except for determination of Baseline as described in Section 5.1 and for the derivation of pharmacokinetic parameters. All other visit and time point collections will be as recorded on the electronic case report forms (eCRFs).

The protocol specifies that dosing with study drug will be on Day 0 with study days based on this date. In the context of the SAP and associated tables, figures, and graphs, study days from this point on will be based off of the day of dosing with the day of dosing being Day 1 and the day prior to dosing being Day -1. i.e., there will no Day 0.

Unless otherwise stated, hypothesis testing will be two-sided with an alpha level of 0.05.

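### The primary MMRM lists baseline WOMAC A only as a main effect, so one baseline slope serves every visit; a baseline-by-visit term could recover a little Week 12 precision at almost no cost

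*SAP*

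**What the plan says.** SAP section 3 (Primary Estimand, Summary Measure) describes the primary model as an MMRM with "fixed effects for treatment, visit, and treatment-by-visit interaction and covariates site, Baseline WOMAC A pain score, and randomization stratification factors". Protocol section 3.3.4 gives "fixed effects for treatment group, study visit, treatment-by-visit interaction, site and baseline covariates", and the protocol synopsis lists the same terms. None of these places has a baseline-by-visit term.

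The synopsis adds that subject enters as a random effect. That is the only statement on within-subject covariance that can be read. No readable text says which visits enter the primary MMRM. The main text of SAP section 4.9 and of protocol section 9.7.2 cannot be read in the public documents.

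Elsewhere the SAP fits the same endpoint one visit at a time. The multiple-imputation sensitivity analysis (section 4.9.1) uses a Week 12 ANCOVA with baseline WOMAC A as a covariate, and section 4.10 plans a separate ANCOVA at each visit through Week 26.

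**The concern.** A baseline score usually predicts an early follow-up score better than a late one, so the slope of change on baseline tends to differ between Week 1 and Week 12. A main effect allows only one slope, a weighted average over the visits in the model. If that average differs from the Week 12 slope, chance baseline imbalance between arms is not fully removed from the Week 12 contrast, and its variance rises.

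Precision on the primary contrast is at stake, and the planned power has little slack. It sits close to 80% at an unadjusted alpha of 0.05. The SAP applies a step-down Dunnett procedure to three doses, and section 4.4 records that the sample size was not increased. The primary analysis would also adjust for baseline more restrictively than its own imputation-based sensitivity analysis. A difference between the two could then reflect the slope restriction as well as missing data.

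**Working it through.** **1. The plan's own power figure.** Inputs from the protocol synopsis: "With approximately 72 evaluable subjects per arm for the primary endpoint (Arms A, B, C, and E), the study is powered at 80"%, a "pain score of 2.0 with standard deviation of 0.59", and assumptions "yielding a difference of 0.28 between the groups". SAP section 4.1 says "hypothesis testing will be two-sided with an alpha level of 0.05".

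- Standard error of a contrast: 0.59 × √(2/72) = 0.0983.
- Power: Φ(0.28/0.0983 − 1.96) = 81.3%, or 80.7% with the noncentral t.
- n for 80%: 2 × (0.59/0.28)² × (1.96 + 0.842)² = 69.7, so 70 per arm.

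The stated 80% with 72 per arm reproduces.

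**2. Variance with the wrong slope.** The Week 12 contrast is the difference in mean change minus β times the difference in mean baseline. If the fitted common slope β differs from the Week 12 slope b₁₂, then

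variance ratio = 1 + (β − b₁₂)² σ_B² / [σ₁₂² (1 − r₁₂²)],

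where r₁₂ is the correlation of the Week 12 score with baseline, and σ_B and σ₁₂ are the baseline and Week 12 SDs.

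**3. Assumptions, none of them in the documents.**
- Correlation with baseline falls linearly in √time from Week 1 to Week 26.
- The follow-up SD equals the baseline SD, or grows to 1.4 times it by Week 26.
- Visits are Weeks 1, 2, 4, 8, 12, 16, 20 and 26 (the list in SAP section 5.1), or the first five of these.
- Visits are weighted in one of two ways. The first is generalised least squares with residual correlation φ^|√s − √t|, φ = 0.6 or 0.8, iterated. The second is equal weights, as a random subject effect with constant residual variance gives for complete data.

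**4. Worked case (0.8 to 0.3, constant SD, visits to Week 26).**
- Fraction of the fall reached by Week 12: (√12 − 1)/(√26 − 1) = 0.601.
- r₁₂ = 0.8 − 0.5 × 0.601 = 0.499, so b₁₂ = 0.499 − 1 = −0.501.
- Generalised least squares with φ = 0.8: common slope −0.277, gap 0.224. Ratio = 1 + 0.0502/0.751 = 1.067. The SE rises by 3.3% and power is 78.7%.
- Equal weights: the mean fraction over eight visits is 0.496, so the gap is 0.5 × (0.601 − 0.496) = 0.052. Ratio = 1 + 0.0027/0.751 = 1.004.
- Equal weights, visits to Week 12: the mean fraction over five visits is 0.278 and the gap 0.161. Ratio = 1 + 0.0260/0.751 = 1.035.

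**5. Week 12 variance loss over all settings (%).**

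| Baseline correlation, Week 1 to Week 26 | GLS, visits to Week 26 | GLS, visits to Week 12 | Equal weights, to Week 26 | Equal weights, to Week 12 |
|---|---|---|---|---|
| 0.6 to 0.5 | 0.0–0.2 | 0.1–0.3 | 0.0 | 0.1 |
| 0.7 to 0.4 | 0.1–1.1 | 0.2–2.2 | 0.0–0.1 | 0.1–1.3 |
| 0.8 to 0.3 | 1.3–6.7 | 2.0–9.6 | 0.0–0.4 | 1.0–3.5 |

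Taking 0.59 as the residual SD with the interaction in the model (81.3% power), power without it for visits to Week 26 under GLS is 80.9% to 81.2% for 0.7 to 0.4, and 78.7% to 80.7% for 0.8 to 0.3. The 9.6% cell (visits to Week 12, constant SD, φ = 0.8) corresponds to about 77.6%.

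**6. Effect on the estimate.** A one-SD chance imbalance in baseline is 0.0983. Multiplied by a gap of 0.088 (the largest for 0.7 to 0.4, visits to Week 26) it moves the contrast by 0.009. With a gap of 0.224 it moves it by 0.022. The planned effect is 0.28.

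**7. Bias check by simulation** (500 trials, 72 per arm, 0.8 to 0.3, true effect −0.28).
- Complete data: common slope −0.286 (empirical SE 0.088), by-visit slope −0.284 (0.084). The Monte Carlo error is about 0.088/√500 = 0.004, so there is no clear bias.
- Strong baseline-dependent dropout in placebo only, 14% missing at Week 12: common slope −0.307, by-visit slope −0.280. The common-slope model is off by about 0.03.

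**The case against.** The strongest reply is that the full model specification cannot be read. Section 3 of the SAP is one cell of an estimand table, and the main primary-analysis text is not visible in either document. An interaction may be specified there. This stands, and it is why the request is to add the term or confirm that it exists. The section 3 list should match in either case.

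Second, the main-effect model is valid under randomisation, and the Week 12 ANCOVA after multiple imputation already has its own slope. Both points are correct. The sensitivity analysis would reveal a material difference, but it is not the primary test and does not restore precision there.

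A reader might infer more than the documents support:

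- **That the slope spans Weeks 1 to 26.** No readable text gives the visit range of the primary MMRM. The model may stop at Week 12.
- **That early visits drive the slope.** This depends on the covariance structure. Under GLS with visits to Week 26, Weeks 1 to 4 carried 46% to 98% of the weight in the three patterns above. Under equal weights they carry 3/8, and the loss is then at most 0.4%. The only structure the documents mention, a random subject effect, points to equal weights if residual variance is constant.
- **That the loss equals a share of the 348 randomised.** Arms D and F are in that total but not in the primary contrasts. Each contrast compares two arms of about 72, or 144 subjects.
- **That least squares means should be evaluated at the mean baseline.** Without a treatment-by-baseline term, the treatment difference is the same at every baseline value.

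**Conclusion.** The point holds as a minor efficiency issue. As listed, the primary model imposes one baseline slope on all its visits. The cost at Week 12 is negligible if the baseline correlation decays weakly (at most 0.3% of variance) and at most about 2% if it decays moderately. Under strong decay it lies between 0.1% or less and about 7%, apart from the one 9.6% setting in which visits stop at Week 12. All of these rest on assumed correlations, SD patterns and covariance structures, because the documents give no correlations and the SAP's covariance structure is not visible.

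It would be tempting to call the primary estimate biased. The documents do not support that: with randomised arms and complete data the common-slope model loses precision only. A small bias needs dropout that depends on baseline and differs between arms. The figure of 0.03 came from a deliberately strong version of that pattern.

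**What to change.** Add a baseline WOMAC A-by-visit interaction to the primary MMRM. If the full specification already contains it, align the term list in SAP section 3 with that text. In the same sentence, state which visits enter the model and which covariance structure is used, since the size of the loss depends on both.

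The cost is one model term: four extra parameters for the five visits to Week 12, or seven for the eight visits to Week 26. No new data are needed, and almost nothing is lost if the slopes turn out equal. The change should be made before unblinding.
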